**APPENDIX 1: TRACK QUESTIONNAIRE**

**TRACK™ Test for Respiratory and Asthma Control in Kids**

**Who should use TRACK?**

This simple test can help determine if your child's breathing problems are not under control.

The test was designed for children who

- Are under 5 years of age **AND**
- Have a history of 2 or more episodes of wheezing, shortness of breath, or cough lasting more than 24 hours **AND**
- Have been previously prescribed bronchodilator medicines, also known as quick-relief medications (eg, albuterol, Ventolin®, Proventil®, Maxair®, ProAir®, or Xopenex®), for respiratory problems **OR** have been diagnosed with asthma

**For kids under 5 years of age**

**How to take TRACK**

**Step 1:** Make a check mark in the box below each of your selected answers.

**Step 2:** Write the number of your answer in the score box provided to the right of each question.

**Step 3:** Add up the numbers in the individual score boxes to obtain your child's total score.

**Step 4:** Take the test to your child's health care provider to talk about your child's total TRACK score.

					Score	
1	During the past 4 weeks , how often was your child bothered by breathing problems, such as wheezing, coughing, or shortness of breath?					□
	Not at all □ 20	Once or twice □ 15	Once every week □ 10	2 or 3 times a week □ 5	4 or more times a week □ 0	
2	During the past 4 weeks , how often did your child's breathing problems (wheezing, coughing, shortness of breath) wake him or her up at night?					□
	Not at all □ 20	Once or twice □ 15	Once every week □ 10	2 or 3 times a week □ 5	4 or more times a week □ 0	
3	During the past 4 weeks , to what extent did your child's breathing problems, such as wheezing, coughing, or shortness of breath, interfere with his or her ability to play, go to school, or engage in usual activities that a child should be doing at his or her age?					□
	Not at all □ 20	Slightly □ 15	Moderately □ 10	Quite a lot □ 5	Extremely □ 0	
4	During the past 3 months , how often did you need to treat your child's breathing problems (wheezing, coughing, shortness of breath) with quick-relief medications (albuterol, Ventolin®, Proventil®, Maxair®, ProAir®, Xopenex®, or Primatene® Mist)?					□
	Not at all □ 20	Once or twice □ 15	Once every week □ 10	2 or 3 times a week □ 5	4 or more times a week □ 0	
5	During the past 12 months , how often did your child need to take oral corticosteroids (prednisone, prednisolone, Orapred®, Prelone®, or Decadron®) for breathing problems not controlled by other medications?					□
	Never □ 20	Once □ 15	Twice □ 10	3 times □ 5	4 or more times □ 0	
The brands mentioned herein are trademarks of their respective owners and are not trademarks of the AstraZeneca group of companies. The makers of these brands are not affiliated with and do not endorse AstraZeneca or its products.					Total	
Please see reverse side for an explanation of what your child's total TRACK score means.					□	

APPENDIX 2A: ASTHMA CONTROL TEST – FOR CHILDREN AGE 5-11 YEARS

# CHILDHOOD ASTHMA CONTROL TEST

For children age 5-12 years of age

## How to take the Childhood Asthma Control Test:

1. Let your child respond to the first four questions (1 to 4), by **CIRCLING THEIR ANSWER**. If your child needs help reading or understanding the question, you may help, but let your child select the response.
2. Complete the remaining three questions (5 to 7) on your own by **CIRCLING YOUR ANSWER**. Try not to let your child’s responses influence your answers. There are no right or wrong answers.

1. How is your asthma today?

 0 Very bad	 1 Bad	 2 Good	 3 Very good
---	--	---	--

2. How much of a problem is your asthma when you run, exercise or play sports?

 0 It's a big problem, I can't do what I want to do.	 1 It's a problem and I don't like it.	 2 It's a little problem but it's okay.	 3 It's not a problem.
--	--	---	--

3. Do you cough because of your asthma?

 0 Yes, all of the time.	 1 Yes, most of the time.	 2 Yes, some of the time.	 3 No, none of the time.
--	---	---	--

4. Do you wake up during the night because of your asthma?

 0 Yes, all of the time.	 1 Yes, most of the time.	 2 Yes, some of the time.	 3 No, none of the time.
--	---	---	--

**Please complete the following questions on your own.**

5. During the last 4 weeks, on average, how many days per month did your child have any daytime asthma symptoms?

5 Not at all	4 1-3 days/mo	3 4-10 days/mo	2 11-18 days/mo	1 19-24 days/mo	0 Everyday
------------------------	-------------------------	--------------------------	---------------------------	---------------------------	----------------------

6. During the last 4 weeks, on average, how many days per month did your child wheeze during the day because of asthma?

5 Not at all	4 1-3 days/mo	3 4-10 days/mo	2 11-18 days/mo	1 19-24 days/mo	0 Everyday
------------------------	-------------------------	--------------------------	---------------------------	---------------------------	----------------------

7. During the last 4 weeks, on average, how many days per month did your child wake up during the night because of asthma?

5 Not at all	4 1-3 days/mo	3 4-10 days/mo	2 11-18 days/mo	1 19-24 days/mo	0 Everyday
------------------------	-------------------------	--------------------------	---------------------------	---------------------------	----------------------

APPENDIX 2B: ASTHMA CONTROL TEST – YOUNG PEOPLE AGE 12+ YEARS

# ASTHMA CONTROL TEST

For young people over 12 years of age

### Why take the Asthma Control Test™?

The Asthma Control Test™ will provide you with a snapshot of how well your asthma has been controlled over the last four weeks, giving you a simple score out of 25. Asthma symptoms can vary from month to month, so it is worth keeping the test handy to see if your score changes. You can also share your results with your doctor or asthma nurse to help explain just how your asthma affects you.

**Are you in control of your asthma? Or is your asthma in control of you? Here's how to find out**

**Step 1:** Read each question below carefully, circle your score and write it in the box.

**Step 2:** Add up each of your five scores to get your total Asthma Control Test™ score.

**Step 3:** Use the score guide to learn how well you are controlling your asthma.

Q1	During the past 4 weeks , how often did your asthma prevent you from getting as much done at work, school or home?	Score:
	
 All of the time 1 Most of the time 2 Some of the time 3 A little of the time 4 None of the time 5 
	
Q2	During the past 4 weeks , how often have you had shortness of breath?	Score:
	
 More than once a day 1 Once a day 2 3-6 times a week 3 1-2 times a week 4 Not at all 5 
	
Q3	During the past 4 weeks , how often did your asthma symptoms (wheezing, coughing, chest tightness, shortness of breath) wake you up at night or earlier than usual in the morning?	Score:
	
 4 or more times a week 1 2-3 nights a week 2 Once a week 3 Once or twice 4 Not at all 5 
	
Q4	During the past 4 weeks , how often have you used your reliever inhaler (usually blue)?	Score:
	
 3 or more times a day 1 1-2 times a day 2 2-3 times a week 3 Once a week or less 4 Not at all 5 
	
Q5	How would you rate your asthma control during the past 4 weeks ?	Score:
	
 Not controlled 1 Poorly controlled 2 Somewhat controlled 3 Well controlled 4 Completely controlled 5 
	

**Total Score**

### What does your score mean?

**Score: 25 – WELL DONE**

- Your asthma appears to have been **UNDER CONTROL** over the last 4 weeks.
- However, if you are experiencing any problems with your asthma, you should see your doctor or nurse.

**Score: 20 to 24 – ON TARGET**

- Your asthma appears to have been **REASONABLY WELL CONTROLLED** during the past 4 weeks.
- However, if you are experiencing symptoms your doctor or nurse may be able to help you.

**Score: less than 20 – OFF TARGET**

- Your asthma may **NOT HAVE BEEN CONTROLLED** during the past 4 weeks.
- Your doctor or nurse can recommend an asthma action plan to help improve your asthma control.

## APPENDIX 3: ASTHMA CONTROL QUESTIONNAIRE

Please answer questions 1–6.

Circle the number of the response that best describes how you have been during the past week

- |   |  |
|---|--|
| 1. On average, during the past week, how often were you woken by your asthma during the night?                            | 0 Never
1 Hardly ever
2 A few minutes
3 Several times
4 Many times
5 A great many times
6 Unable to sleep because of asthma                            |
| 2. On average, during the past week, how bad were your asthma symptoms when you woke up in the morning?                   | 0 No symptoms
1 Very mild symptoms
2 Mild symptoms
3 Moderate symptoms
4 Quite severe symptoms
5 Severe symptoms
6 Very severe symptoms                |
| 3. In general, during the past week, how limited were you in your activities because of your asthma?                      | 0 Not limited at all
1 Very slightly limited
2 Slightly limited
3 Moderately limited
4 Very limited
5 Extremely limited
6 Totally limited              |
| 4. In general, during the past week, how much shortness of breath did you experience because of your asthma?              | 0 None
1 A very little
2 A little
3 A moderate amount
4 Quite a lot
5 A great deal
6 A very great deal   |
| 5. In general, during the past week, how much of the time did you wheeze?   | 0 Not at all
1 Hardly any of the time
2 A little of the time
3 A moderate amount of the time
4 A lot of the time
5 Most of the time
6 All the time     |
| 6. On average, during the past week, how many puffs of short-acting bronchodilator (eg. Ventolin) have you used each day? | 0 None
1 1–2 puffs most days
2 3–4 puffs most days
3 5–8 puffs most days
4 9–12 puffs most days
5 13–16 puffs most days
6 More than 16 puffs most days |

To be completed by a member of the clinic staff

- |  |                  |
|--|------------------|
| 7. FEV 1 pre-bronchodilator: .....          | 0 >95% predicted |
| FEV 1 predicted .....                       | 1 95–90%         |
| FEV 1 % predicted .....                     | 2 89–80%         |
| (Record actual values on the dotted lines              | 3 79–70%         |
| and score the FEV 1 % predicted in the next | 4 69–60%         |
| column)  | 5 59–50%         |
|  | 6 <50% predicted |

©The Asthma Control Questionnaire is copyrighted. It may not be changed, translated or sold (paper or software) without the permission of Elizabeth Juniper.

#### APPENDIX 4: BRIGHTON COLLABORATION CASE DEFINITION OF ANAPHYLAXIS

Anaphylaxis is a clinical syndrome characterized by:

- sudden onset AND
- rapid progression of signs and symptoms AND
- involving multiple ( $\geq 2$ ) organ systems, as follows:

Level 1 of diagnostic certainty
 
 
• <math>\geq 1</math> major cardiovascular AND/OR <math>\geq 1</math> major respiratory criterion AND
 
• <math>\geq 1</math> major dermatological criterion
 

Level 2 of diagnostic certainty
 
 
• <math>\geq 1</math> major cardiovascular AND <math>\geq 1</math> major respiratory criterion OR
 
• <math>\geq 1</math> major cardiovascular OR respiratory criterion AND
 
• <math>\geq 1</math> minor criterion involving <math>\geq 1</math> different system (other than cardiovascular or respiratory systems) OR
 
• (<math>\geq 1</math> major dermatologic) AND (<math>\geq 1</math> minor cardiovascular AND/OR minor respiratory criterion)
 

Level 3 of diagnostic certainty
 
 
• <math>\geq 1</math> minor cardiovascular OR respiratory criterion AND
 
• <math>\geq 1</math> minor criterion from each of <math>\geq 2</math> different systems/categories
 

Note that all levels of diagnostic certainty **require the involvement the cardiovascular and/or respiratory systems.**

Organ System	Major Criteria	Minor Criteria
Skin or mucosal	
 
• generalized urticaria (hives) or erythema
 
• angioedema, localized or generalized
 
• generalized pruritus with skin rash
 
	
 
• generalized pruritus without skin rash
 
• generalized prickle sensation
 
• localized injection site urticaria
 
• red and itchy eyes
 

Cardiovascular	
 
• measured hypotension OR
 
• shock (at least 3 of the following):               
 
▪ tachycardia
 
▪ capillary refill time (CRT) <math>>3</math> sec
 
▪ reduced central pulse volume
 
▪ decreased level or loss of consciousness
 
 
 
	
 
• Reduced peripheral circulation (at least 2 of:               
 
• Tachycardia
 
• CRT <math>>3</math> sec without hypotension
 
• Decreased level of consciousness
 
 
 

Respiratory	
 
• Bilateral wheeze (bronchospasm)
 
• Stridor
 
• Swelling of upper airways
 
• Respiratory distress (at least 2 of tachypnoea; use of accessory respiratory muscles; recession; cyanosis; grunting)
 
	
 
• Persistent dry cough
 
• Hoarse voice
 
• Difficulty breathing without wheeze or stridor
 
• Sensation of throat closure
 

Gastrointestinal		
 
• Diarrhoea
 
• Abdominal pain
 
• Nausea
 
• Vomiting
 

Laboratory		Mast cell tryptase $>$ upper normal limit

NB: For the purposes of this study, local rhinitis and oropharyngeal symptoms will be classed as LOCAL symptoms and not indicative of a systemic allergy response.

**APPENDIX 5: TOPIC GUIDE FOR 72HR TELEPHONE FOLLOW-UP**

*Participants' families will be contacted by the local research team at least 72 hours after LAIV administration (and within 7 days, to allow for weekends), to determine whether their child has experienced any delayed symptoms which might be attributable to the vaccine. This telephone consultation will take approximately 2-3 minutes. If after three attempts (on three separate days) the local study team is unable to contact the family, the child will be deemed lost to follow up.*

**Guide to telephone interview:**

1. Confirm interviewee's identity

2. Introduce yourself:

*"I am <name>, from the SNIFFLE-4 Study. We arranged to speak briefly today to find how <participant's name> is going after his/her 'flu vaccine on <date>"*

3. *"Have you noticed any health problems since the vaccine?"*

4. For each symptom reported:

- *When did this start?*
- *How long did this last?*
- *Did you do anything as a result?*

5. *"Since the vaccine,*

- i. Have you needed to give your child more reliever medicine (e.g. ventolin) than normal?*
- ii. Have you had to take <participant's name> to see a Doctor because of his/her breathing?*
- iii. (If YES) – did you have to take them to hospital?*
- iv. (If YES) – did <participant's name> have to stay in hospital overnight?*
- v. Did <participant's name> have to start any medicines, like an oral steroid? If so, for how long?*

**FINALLY: Remind family to take nasal swab at 72 hours and 6 days after LAIV.**

**APPENDIX 6: TOPIC GUIDE FOR TELEPHONE FOLLOW-UP AT 4 WEEKS**

**\*\* For patients with asthma/recurrent wheeze only \*\***

*Participants' families will be contacted by the local research team 4 weeks after LAIV administration, to determine whether their child has experienced any change in their lower respiratory symptoms which might be attributable to the vaccine. This telephone consultation will take approximately 2-3 minutes. If after three attempts (on three separate days) the local study team is unable to contact the family, the child will be deemed lost to follow up.*

**Guide to telephone interview:**

1. Confirm interviewee's identity

2. Introduce yourself:

*"I am <name> from the SNIFFLE-4 Study. Your child <participant's name> had the 'flu vaccine with us one month ago, and we arranged to speak to find out if you had needed to do anything different with his asthma/wheezing"*

3. Complete appropriate TRACK / C-ACT / ACT Questionnaire over the telephone

(see separate questionnaires)

4. Finally, ask the following questions:

*Since the vaccine,*

*i) Have you had to take <participant's name> to see a Doctor because of his/her breathing?*

*ii) (If YES) – did you have to take them to hospital?*

*iii) (If YES) – did <participant's name> have to stay in hospital overnight?*

*iv) Did <participant's name> have to start any medicines, like an oral steroid? If so, for how long?*

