#### 8.1.3 ASTHMA CONTROL ASSESSMENT PRE AND 4 WEEKS POST VACCINATION

Participants' families will be asked to complete a questionnaire to determine their child's asthma symptoms and control, using a validated tool at visit 1:

- In children age 2-4 years: TRACK questionnaire (Appendix 1)
- In children age 5-11 years: C-ACT questionnaire (Appendix 2a)
- In children age 12+ years: ACT questionnaire (Appendix 2b)

As part of the CRF, the questions on the Asthma Control Questionnaire (ACQ, Appendix 3) will also be completed. While the (C-)ACT and TRACK questionnaires assess asthma symptoms over the preceding 4 weeks, the ACQ assesses symptoms and control over the preceding 7 days and also includes lung function; the ACQ may therefore be more representative of asthma control at the time of vaccination. The (C-)ACT will be completed first, before the ACQ.

Families will be asked to complete a further questionnaire 4 weeks after vaccination. In general, this will be done using an online questionnaire. Families will be asked at their first

visit as to whether they prefer to be contacted by telephone by the study team, or receive an email request with a link to a secure, online survey. Either way, the survey will take 2-3 minutes to complete. A guide for the telephone call is provided in Appendix 6. These data will be recorded on a CRF.

If the family fails to respond to the email request, the local study team will attempt to contact the family by telephone. If, after three attempts (on three separate days), the local study team is unable to contact the family, the child will be deemed lost to follow up and this will be documented on the CRF, which will then be closed.

At the Royal Brompton, participants will be invited to return to hospital for the 4 week follow-up (which will, in general, coincide with a routine clinic follow-up appointment). The follow-up questionnaires will be completed at this visit, along with some further repeat assessments (section 8.3).

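### The week-4 telephone script mentions the vaccine and a possible change in asthma care just before the primary questionnaire, an avoidable pre/post asymmetry for families followed up by telephone

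*Combined protocol and SAP*

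**What the plan says.** Appendix 6 sets out the four-week call in numbered steps. After confirming identity, the caller says that the child "had the 'flu vaccine with us one month ago" and that "we arranged to speak to find out if you had needed to do anything different with his asthma/wheezing". Step 3 is "Complete appropriate TRACK / C-ACT / ACT Questionnaire over the telephone". Questions about events since vaccination come only at step 4 ("Finally, ask the following questions"). An introductory note for staff describes the purpose of the call as finding "any change in their lower respiratory symptoms which might be attributable to the vaccine"; that phrase is not part of the spoken text.

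The baseline questionnaire is completed "using a validated tool at visit 1" (Section 8.1.3), and no spoken opening is given for it.

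Telephone is the secondary route at week 4: "In general, this will be done using an online questionnaire". It is used when the family prefers it (8.1.3), has no email (6.1.1) or does not answer: "If the family fails to respond to the email request, the local study team will attempt to contact the family by telephone". Royal Brompton participants are invited to complete the questionnaires at a return visit. Section 9.3 tests the pre/post change with McNemar's test and plans no analysis by mode of completion.

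**The concern.** The study is non-randomised and has no unvaccinated comparison group (Sections 3 and 4). The primary test therefore attributes to the four weeks after vaccination anything that differs systematically between the two questionnaires. The outcome is largely subjective recall. ACT asks for a self-rating of control and for reliever use, and TRACK also asks about reliever use. A sentence about needing something different for asthma touches the same content, and telephone families hear it just before answering.

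If even a small net share of those families then report slightly worse control, the worse cell of the McNemar table grows with no vaccine effect. A safety study could then report a deterioration that is open to the objection that the caller prompted it. The sentence is also not needed to collect events, because step 4 already does that.

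**Working it through.** **1. The passages side by side**

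| | Baseline | Week 4, telephone | Week 4, online |
|---|---|---|---|
| Where | Visit 1 (8.1.3) | Appendix 6 | 8.1.3, 6.1.1 |
| Scripted words before the questionnaire | None given | Vaccine named, then whether anything different was needed for asthma | None given |
| Event questions | Not applicable | After the questionnaire (step 4) | Not described |

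The asymmetry is on the page. Its effect on scores is not.

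**2. The plan's own figure**

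Section 9.2 gives 400 per group for 10% improving against 17.5% deteriorating (5% significance, 80% power). This point does not dispute that figure; it serves to check the formula. With discordant total p = 0.275 and difference d = 0.075, McNemar power is Φ[(d√n − 1.96√p) / √(p − d²)]. This gives 81.9% with 400 pairs and 77.7% with 360 (400 less 10% attrition). So 400 fits McNemar's test before attrition is taken off.

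**3. Illustration: one severity group**

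Inputs:
- background of 10% better and 10% worse (9.2, from SNIFFLE-2);
- n = 0.89 × 420 = 374 (target in Section 3, SNIFFLE-2 follow-up in 9.2);
- two-sided 5% test;
- assumed net shift d from no change to worse, so p = 0.20 + d.

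The same formula gives the probability of a significant result in the worse direction. For d = 0.01: (0.01 × √374 − 1.96 × √0.21) / √(0.21 − 0.0001) = (0.193 − 0.898) / 0.458 = −1.54, so the probability is 6.2%.

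| Net shift into worse | False significantly-worse, n = 374 |
|---|---|
| 0 | 2.5% |
| 0.5 points | 4.0% |
| 1 point | 6.2% |
| 2 points | 12.8% |
| 3 points | 22.6% |

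Simulation agrees to within about 0.2 percentage points.

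**4. What a given shift requires**

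The net shift is f × s, where f is the share telephoned and s is the net share of those moved into worse. Both are assumptions. With n = 360, total two-sided rejection of the nominal 5% test is:

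| | s = 2% | s = 5% | s = 10% |
|---|---|---|---|
| f = 10% | 5.1% | 5.5% | 7.0% |
| f = 25% | 5.5% | 8.1% | 17.0% |
| f = 50% | 7.0% | 17.0% | 47.5% |

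The distortion is negligible when few families are telephoned. It is large only when telephone use is common and the wording moves many of them.

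**The case against.** The case on the other side is substantial.

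- **The spoken words are mild.** They ask about a different need, which could mean less treatment, and mention neither worsening nor causation. The attribution wording is in the staff note. This stands: a reader might infer that the script tells parents the vaccine may have worsened asthma, and it does not.
- **Telephone is the secondary mode.** This stands, although three routes lead to it and the documents cap none of them.
- **The 72-hour call already sensitises families.** Appendix 5, planned for every family, asks about health problems since the vaccine, extra reliever use and doctor visits for breathing. This stands: later online responders hear it too, so rewording Appendix 6 would not remove all pre/post asymmetry. But that call collects early adverse events and needs those questions; the Appendix 6 opening does not need its sentence.
- **The instruments limit the effect.** Children answer C-ACT items 1–4, ACT is worded for the young person, and TRACK items 4 and 5 look back 3 and 12 months. A child must also pass both a change threshold and a cut-off to count as worse. This makes a large shift less likely, but does not exclude a small one.
- **The percentages rest on an assumed shift.** True. They show sensitivity and do not estimate bias.
- **Mode could be examined in the analysis.** Partly true. Families are not randomised to mode, so such an analysis cannot separate the wording from the kind of family that gets telephoned.

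**Conclusion.** The point holds as an avoidable asymmetry in how the primary outcome is collected, limited to families who complete week 4 by telephone. Worsening is the plausible direction, because needing to do something different suggests extra care, but that is inference.

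A reader might go further and conclude that telephone scores are shown to be biased towards worsening, or that the false-positive rate will be 13% or 23%. The documents do not support either reading. They report no mode or wording effect and no telephone share, and those percentages require an assumed net shift of 2 or 3 points. At a 10% telephone share with 5% of those families tipped, total rejection is 5.5% instead of 5%.

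The comparison of severe with non-severe children is biased only if telephone use or the effect of the cue differs by severity. If the effect does run towards worsening, it would tend to create a false alarm.

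The change is still worth making: the asymmetry is certain, its size is unknown, and removing it costs almost nothing.

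**What to change.** 1. Replace the purpose sentence in Appendix 6, step 2, with a neutral opening, for example: *we arranged to go through the same breathing questionnaire that was completed at your visit*. Remove the mention of the vaccine from that step.
2. Keep TRACK, C-ACT or ACT as the first substantive item. Mention the vaccine and any change in care only at step 4, where the event questions already are.
3. Record the mode of completion at week 4 (online, telephone or in person). Add to Section 9.3 a sensitivity analysis of the primary outcome by mode, with a note that mode is self-selected.

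The cost is a reworded opening, one data field and one extra table. No visit, staff time or event data are lost, and no clinical rule changes. The Appendix 5 call can stay as it is, but the report should acknowledge that it sensitises all families.

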### 3.1.2. SECONDARY STUDY OUTCOMES

1. Incidence of adverse events (AE) and serious adverse events (SAEs) in children receiving LAIV:
  - AEs occurring up to 72 hours after LAIV.
  - SAEs unrelated to asthma symptoms with onset up to 72 hours after LAIV
  - Incidence of a 'significant exacerbation' in asthma, defined as:
    - i. At least 3 day course of oral steroids following an unscheduled contact with a healthcare professional; OR
    - ii. Unscheduled visit to an Emergency department or admission to hospital for treatment of asthma symptoms, requiring systemic corticosteroids
2. Incidence and extent of viral shedding in children and young people receiving LAIV during the 2016/17 influenza season, using quantitative analysis of consecutive nasal swabs obtained up to 10 days following LAIV. These data will be correlated with the incidence of adverse events related to asthma over the same time period.

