### 4.2.2 EXCLUSION CRITERIA

1. **Admission to PICU for invasive ventilation due to a respiratory illness in the preceding 2 years.**
2. **Contraindications to LAIV** (notwithstanding allergy to egg protein), which include:
  - a. Hypersensitivity to the active ingredients, gelatin or gentamicin (a possible trace residue)
  - b. Previous systemic allergic reaction to LAIV
  - c. Previous allergic reaction to an influenza vaccine (not LAIV) is a relative contra-indication, which must be discussed with the site PI to confirm patient suitability
  - d. Children/adolescents who are clinically immunodeficient due to conditions or immunosuppressive therapy such as: acute and chronic leukaemias; lymphoma; symptomatic HIV infection; cellular immune deficiencies; and high-dose corticosteroids\*\*.  
**\*\*High-dose steroids** is defined as a treatment course for at least one month, equivalent to a dose *greater than* 20mg prednisolone per day (any age), or for children under 20kg, a dose *greater than* 1mg/kg/day.  
NB: LAIV is not contraindicated for use in individuals with asymptomatic HIV infection; or individuals who are receiving topical/inhaled/low-dose oral systemic corticosteroids or those receiving corticosteroids as replacement therapy, e.g. for adrenal insufficiency.
  - e. Children / adolescents younger than 18 years of age receiving salicylate therapy because of the association of Reye's syndrome with salicylates and wild-type influenza infection.
  - f. Pregnancy

3. **Contraindications to vaccination on that occasion**, e.g. due to child being acutely unwell:
- Febrile  $\geq 38.0^{\circ}\text{C}$  in last 72 hours
  - \*Acute wheeze in last 72 hours requiring treatment beyond that normally prescribed for regular use by the child's treating healthcare professional
  - \*Recent admission to hospital in last 2 weeks for acute asthma
  - \*Current oral steroid for asthma exacerbation or course completed within last 2 weeks
  - Any other significant condition or circumstance which, in the opinion of the investigator, may either put the participant at risk because of participation in the study, or may influence the result of the study, or the participant's ability to participate in the study.

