### 9.2 SAMPLE SIZE ESTIMATION

Sample size is based on the primary objective of comparing the proportion of participants who experience a significant change in asthma control, as measured by a change in at least 3 points *and* from  $\geq 20$  on the (C-)ACT (good control) to  $< 20$  (sub-optimal control) in each group (BTS  $\leq 3$  vs BTS 4/5), or vice versa. In the SNIFFLE-2 study, such a change (one way or the other) was seen in about 20% of children (10% worse, 10% better).

A sample of 400 children in each group will provide sufficient power (5% significance level, 80% power) to detect an improvement in 10% vs deterioration in 17.5%, allowing for 10% attrition. In SNIFFLE-2, follow-up at four weeks was 89%. If the proportion of participants with a change in ACT score is less than this, with only 5% improving and 10% getting worse, a sample size of about 420 would provide a similar level of power. This would represent a conservative assumption in the proportions changing. For comparing the average change pre to post vaccination in ACT score between the severe and non-severe groups, the standard deviation of change from SNIFFLE-2 was used (about 3 units). With a sample size of 400 in each group the detectable difference is 0.6 units between the groups (80% power, 5% significance).

Assuming that about 1% of participants experience a significant deterioration in asthma control (as defined in 3.1.2 above), then the 95% CI for a significant deterioration will be from 0.027% to 2.54%. If 0/400 are observed the upper 95% CI is 0.92%.

---

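### Follow-up asks whether an oral steroid was started, so an exacerbation treated by raising a maintenance oral steroid can go unrecorded

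*Combined protocol and SAP*

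**What the plan says.** **Who can enrol.** Section 4.2.2 lists immunosuppression from high-dose corticosteroids as a contraindication, limited to courses of at least a month above a stated daily dose. Its note says the vaccine is not contraindicated in "individuals who are receiving topical/inhaled/low-dose oral systemic corticosteroids or those receiving corticosteroids as replacement therapy". A child on maintenance low-dose oral steroid is therefore eligible.

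**What counts.** Sections 3.1.2 and 9.1 define a significant exacerbation by two limbs. Limb (i) is "At least 3 day course of oral steroids following an unscheduled contact with a healthcare professional". Limb (ii) is an unplanned emergency department attendance or an admission for asthma in which systemic corticosteroids were needed. Both limbs depend on steroid information. Neither says how to treat a child who takes oral steroids every day.

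**How it is ascertained by telephone.** Appendix 5 (item v of the breathing questions) and Appendix 6 (item iv) use the same steroid question, limited to the time since vaccination: did the child "have to start any medicines, like an oral steroid? If so, for how long"? The other items ask about seeing a doctor, going to hospital and staying overnight. Appendix 5 also asks whether more reliever than normal was needed.

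**How it is used.** Section 9.3 estimates the exacerbation incidence with 95% confidence intervals, compares secondary outcomes with historical rates by Fisher's exact test, plans severe and non-severe subgroups, and uses significant exacerbation as the target of the ROC analysis.

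**The concern.** The definition and the question share a blind spot. If a child already takes an oral steroid and the dose is raised for some days after an unscheduled contact, nothing has been started. The parent can answer no and be correct. The contact questions may show that a doctor was seen, but contact alone satisfies neither limb. Even if the increase is mentioned, the definition does not tell the assessor whether it is a course, or whether an emergency attendance required systemic steroids in a child who takes them daily.

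The protocol handles relievers better: Appendix 5 asks about use above normal. The steroid question, which bears directly on the outcome, has no equivalent.

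Section 1.3 gives the lack of safety data in children on the most intensive treatment as the reason for the study. Section 9.2 plans on about 1% of participants having the event, roughly 4 in 400, so one or two unrecorded events would be visible in the estimate.

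**Working it through.** **1. The plan's own precision figure.** Section 9.2 assumes 1% with the event and gives a 95% interval of 0.027% to 2.54%, and an upper limit of 0.92% for 0/400. Exact (Clopper-Pearson) limits are:

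- 4/400: 0.273% to 2.54%
- 0/400: upper limit 0.918%

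Both upper limits reproduce. The lower limit does not; 0.027% looks like a decimal slip for 0.27%. It should be checked, but nothing below depends on it.

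**2. Inputs for the possible under-count.**

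- N = 400 severe children (the group size in section 9.2; the target in section 3 is 420)
- r = 1% event rate in children not on maintenance oral steroids (section 9.2)
- m = share of the severe group on maintenance oral steroids. Not in the documents; assumed 2% to 20%
- RR = event rate in those children relative to r. Assumed 1 to 5
- f = fraction of their events that the follow-up misses. Assumed 0.5 to 1

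**3. Formulas.**

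- Events missed = N × m × r × RR × f
- True events = N × r × (1 − m + m × RR)

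**4. Results.**

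| m | Fewest missed (RR 1, f 0.5) | Most missed (RR 5, f 1) | Share of true events |
|---|---|---|---|
| 2% | 400 × 0.02 × 0.01 × 1 × 0.5 = 0.04 | 0.4 | 1% to 9% |
| 5% | 0.1 | 400 × 0.05 × 0.01 × 5 × 1 = 1.0 | 2.5% to 21% |
| 10% | 0.2 | 2.0 | 5% to 36% |
| 20% | 0.4 | 400 × 0.20 × 0.01 × 5 × 1 = 4.0 | 10% to 56% |

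**5. The worst corner.** With m = 20%, RR = 5 and f = 1, true events are 400 × 0.01 × (0.8 + 0.2 × 5) = 7.2 (1.8%). Recorded events are 7.2 − 4.0 = 3.2 (0.8%). For scale, the exact interval is 0.71% to 3.57% for 7/400 and 0.15% to 2.18% for 3/400. The point estimate would more than halve, although the intervals overlap.

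**The case against.** The strongest reply is that the steroid question does not stand alone.

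- **Other prompts.** The 4-week guide opens by asking whether the family had to manage the asthma differently, then asks about doctor and hospital contact. The 72-hour guide asks of each symptom, "Did you do anything as a result". These are topic guides used by site staff, so a dose increase may come up, and a parent may describe a rescue course as a new medicine. This stands: events can be missed, not must be. But the per-symptom prompt belongs to the early call, and no item in either guide asks about an increased oral steroid.
- **Serious adverse events.** Respiratory SAEs are collected to one month (section 7.1), and the SAE form records corrective treatment (section 7.3.2). This largely covers admissions. It leaves exposed mainly events treated in the community or in an emergency department without admission.
- **The online form.** Sections 6.1.1 and 8.1.3 make an online questionnaire the usual 4-week route. Its steroid items are not shown, so it may already ask the right question. That is a reason to check it; the telephone guides still need correcting.
- **Baseline and TRACK data.** Current medication is collected (section 10.1), but no follow-up question refers back to it. TRACK item 5 covers oral steroids over 12 months, at age 2–4 only, so it does not isolate the period after vaccination.

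A reader might also infer that a child vaccinated during an acute course, which is possible because "Current oral steroid for asthma exacerbation or course completed within last 2 weeks" is only a relative contraindication, could be scored either way. The guides largely answer this: they ask what was started since the vaccine, and a course already running was not.

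**Conclusion.** The gap is real but limited. The eligibility note, the starting-a-medicine wording and a definition silent on dose increases together allow some exacerbations to go unrecorded, mainly those managed without admission. The secondary exacerbation rate and the ROC analysis are affected. The change in TRACK, C-ACT or ACT score is not.

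Under the stated assumptions the loss is about 0.04 to 4 events per 400 severe children, and at most 1 if the share on maintenance oral steroids is 5% or less. That share, the relative rate and the fraction missed are all assumed; the documents fix none of them.

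Three stronger readings are tempting and are not supported:

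- **That the severe group is under-counted while the non-severe group is fully counted.** A lean towards the severe group is plausible, but the readable text does not place maintenance oral steroids at a BTS step (the step figures were not available in the copy reviewed), and it does not say how many such children will enrol.
- **That the loss could exceed the whole expected count.** Taking 20% of 420 (84 children) at a 10% risk gives 8.4 events against a planned 4. But the same assumptions raise the true total to 8.4 + 336 × 1% = 11.8, so 4 is the wrong comparator.
- **That the historical comparison is biased towards reassurance.** The direction depends on how the earlier studies asked about steroids, which the documents do not show.

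**What to change.** These changes concern measurement and outcome counting only; treatment is untouched.

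1. In Appendix 5 item v and Appendix 6 item iv, ask: *Since the vaccine, did the child have to start, or take more than usual of, an oral steroid? For how many days?* Check that the online 4-week form asks the same, and amend it if not.
2. At visit 1, record any maintenance oral steroid and its usual dose under current medication, as the reference for that question.
3. In sections 3.1.2 and 9.1, state that for outcome counting an increase over the usual dose after LAIV is treated in the same way as a new course, in both limbs.
4. Report the exacerbation rate under this definition and, alongside it, counting new courses only.

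The cost is wording in two definitions and two telephone guides, a check of the online form and one baseline item. No extra contact is needed. The downside is that the rate may be slightly higher and less directly comparable with earlier studies; item 4 deals with that.
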